NCT04893265 | Document Date: March 15, 2025

Getting Asian Americans INFORMED to Facilitate COVID-19 Testing and Vaccination

Study Protocol

Table of Contents:

OBJECTIVE	1
STUDY DESIGN	1
METHODS	2
Academic and Community Partnership	2
Participants Eligibility	2
Participants Recruitment and Payment Incentives	2
Procedures	2
Enrollment & Informed Consent	3
Randomization	3
Intervention Group Activities	3
Control Group Activities:	4
STATISTICS ANALYSIS PLAN	5
Primary Outcome Analysis	5
Secondary Outcome Analysis	5

Objective

The INFORMED study aimed to support Chinese, Vietnamese, and Hmong Americans with up-to-date information in multiple languages related to COVID-19 testing.

The acronym INFORMED stands for "Individual and Family Oriented Responsive Messaging Education." The study aimed to deliver updated information that keeps pace with the rapidly changing landscape of COVID-19. Additionally, the messages were adapted accordingly to the feedback received from community members to ensure its relevance and understandability. The ultimate objective was to empower these communities to make informed decisions regarding safety practices and testing for COVID-19.

Study Design

The INFORMED study was conducted as a randomized controlled trial (RCT) involving 247 RCT participants with assessments at baseline, weeks 4, 8, 12 and 16. All participants received intervention via SMS text messaging. Participants who were randomly assigned to the intervention group received educational outreach from lay health workers (LHW) through Zoom or other mutually agreed online video conferencing platforms or in-person adhering to the local COVID-19 social gathering safety practice, as well as by telephone or instant messaging.

Methods

Academic and Community Partnership

The INFORMED study team consisted of researchers from the University of California and three community-based organizations: the Chinese Community Health Resource Center (CCHRC), The Fresno Center (TFC), and the Immigrant Resettlement and Cultural Center (IRCC). Each community partnering agency has a long history of serving their respective targeted communities: Chinese (CCHRC), Hmong (TFC), and Vietnamese (IRCC). In addition, a Community Advisory Board (CAB) included 7 members with expertise in health education, medicine, public health, media communications, social services, and immigrant health. CAB members provided valuable insights into the evolving community needs and ensured the cultural relevance and appropriateness of the study materials, facilitating effective information delivery and outreach to Chinese, Hmong, and Vietnamese American community members.

Participants Eligibility

The inclusion criteria for participants in the randomized controlled trial (RCT) were: i) age 18 and older; ii) self-identified as Chinese, Hmong, or Vietnamese; iii) ability to read and/or speak English, Chinese (Cantonese/Mandarin), Hmong, or Vietnamese; iv) access to a mobile phone to receive SMS text messages (participants received reimbursement if their mobile phone had limited SMS services); v) access to a telephone to be contacted by research staff (to obtain informed consent) and/or by Lay Health Workers (LHWs) for educational sessions when video conferencing on mobile or computer devices was not available.

Participants Recruitment and Payment Incentives

Recruitment utilized multi-pronged strategies proven effective in previous trials involving LHW outreach in various Asian communities. Trained LHWs initially reached out to their social networks. Partnering agencies conducted recruitment through their client population via social media announcements or various events. The program was described as the "Healthy Family Project," focusing on staying healthy by getting informed about COVID-19 testing updates. Each participant received up to \$70 for completing all the surveys online: \$20 for the baseline survey (15-20 minutes long), \$10 for each brief survey at weeks 4, 8, and 12 (5-10 minutes), and \$20 for the final survey at week 16 (15-20 minutes) for outcome evaluation.

Procedures

All study procedures and contacts were conducted in the participants' preferred language: English, Chinese (Cantonese or Mandarin), Hmong, or Vietnamese. The procedures were reviewed and approved by the Institutional Review Board (IRB) at the University of California, San Francisco.

Enrollment & Informed Consent

Interested participants were provided a URL to complete an eligibility survey. Once eligibility was confirmed, participants were provided an informed consent form describing the study, which they signed online to indicate their willingness to participate. Those who had questions about the informed consent form and/or their participation in the study could contact the research staff, who provided the needed information in the language they preferred. Once informed consent was obtained, participants completed a baseline survey where they indicated whether they would be participating individually or with a partner (friend or family member) together in the study.

Randomization

Randomization took place at the individual level. A randomization unit consisted of either an individual participating alone or with a partner to form a dyad and was stratified by partnering agency/Asian ethnicity. Prior to randomization, participants chose their mode of participation (individually or with a partner as a dyad). Randomization occurred after the completion of the baseline assessment. Participants were assigned to either the INFORMED intervention group, which received both LHW educational outreach and a 12-week automated SMS text messaging intervention, or the control group, which received only the SMS text messaging program without LHW support.

Intervention Group Activities

Participants assigned to the intervention group received the INFORMED intervention (described below). They were assessed via online follow-up surveys with links and reminders delivered by SMS at weeks 4, 8, 12, and 16. Each participant will receive up to \$70 for completing all the surveys as described earlier (Participant recruitment and payment incentives).

The INFORMED intervention consisted of two components:

1. Lay Health Worker (LHW) outreach/support providing responsive education and support, and
2. a 12-week automated SMS text messaging program.

Intervention Component #1:

The LHW educational outreach component included 2 small group educational sessions and 2 individual follow-up calls. The small group sessions were delivered via video calls using Zoom or other mutually agreed platforms. Each LHW outreach session, lasting under 1 hour, involved 2 to 6 participants. The sessions included presentations on COVID-19 testing and related information (including vaccination and safe practices) aimed at enhancing participants' understanding of updated COVID-19 testing information, informing them about free testing availability, and motivating them to get tested. Sessions were spaced approximately 1 month apart, with follow-up calls conducted within 2 weeks after each session. Thus, the 4 LHW outreach contacts (group sessions and follow-up calls) were completed within 6 to 8 weeks. Participants who chose to participate as a dyad attended the sessions together. The educational sessions utilized culturally

appropriate PowerPoint presentations with simple texts and images to present current information on:

- COVID-19 testing,
- reasons for getting tested,
- current testing guidelines/who should be tested,
- types of tests available (e.g., antigens and antibodies tests using nose swabs and saliva tests),
- understanding test results (positive versus negative) and the limitations of tests (false negatives),
- the importance of repeated testing, and addressing barriers to testing.

LHW sessions provided a socially and culturally acceptable platform for participants to share personal stories, ask questions, and address concerns. At the end of each session, participants were encouraged to choose an "action item" from their 'Healthy Action Plan' to enhance their knowledge and/or make informed decisions about testing, and if appropriate, take steps toward getting tested (such as identifying test sites). LHW outreach education is responsive to both culture and the rapid changing landscape of the pandemic situation as our intervention contents will be updated accordingly.

Intervention Component #2:

The 12-week automated SMS text messaging component sent weekly messages covering topics taught in the LHW educational outreach sessions. Designed as non-intensive, weekly contact updates, participants received approximately 2 messages on the 6 topics described in the LHW education curriculum. Each message included a link to the full information on the study website "INFORMED."

Messages were responsive to the rapidly evolving developments and changes related to COVID-19 testing guidelines. Participants were notified by text when free testing resources became available in their county. Thus, there were at least 12 pre-programmed messages, along with additional messages responsive to updates in testing resources and related advancements.

All intervention group participants

Control Group Activities:

The control group participated in a 12-week SMS text messaging program only, without LHW educational outreach (as described in Intervention Component #2). The SMS text messaging intervention was identical to that received by the INFORMED participants. All control participants were assessed on the same schedule: baseline, weeks 4, 8, 12, and 16. They received the same amount of incentives (\$70 for completing all assessments).

Statistics Analysis Plan

We conducted our primary outcome using multilevel mixed effects models, controlling for baseline values and incorporating relevant covariates. Additional details of the statistical methods, covariates, and model specifications are provided below. All analyses were conducted using SAS.

Primary Outcome Analysis

1) Primary Outcome

Decisional Conflict for Getting Tested for COVID-19 measured by "SURE" score

2) Model Construction

- a) **Multilevel Mixed Effects Model:** Using GLIMMIX procedure of SAS, we constructed the final multilevel mixed effects model to analyze the primary outcome at week 16 by treatment group (LHW + text message or text message alone). These models were adjusted for the baseline value of the outcome variable and include a random effect to account for participant clustering.
- b) **Model Specification:**
 - i) Fixed Effects: Treatment group, baseline outcome value, covariates at individual, interpersonal and community levels.
 - ii) Random Effects: Participant cluster (random intercepts for participation mode: individual vs dyad)

3) Covariates

- a) **Individual-Level Covariates:** Asian cultural groups, age, sex at birth, current employment status, education, health insurance, self-rated health, preferred language (English vs non-English)
- b) **Interpersonal-Level Covariates:** marital status, household type (family with kids, multigenerational, and no kids/others)
- c) **Community-Level Covariates:** COVID cases per 100,000 populations (matched participants' county and month of survey date), California Healthy Place Index

The following covariates were considered but were not included in the final model due to multicollinearity with other covariates: English proficiency and nativity (highly correlated with preferred language), and income (correlated with current employment status)

Secondary Outcome Analysis

Additional models were constructed to analyze secondary outcomes at week 16: COVID-19 testing receipt (proportion of participants received COVID-19 testing during the past 30 days); intention for getting COVID-19 testing as much as needed; and "SURE" score for getting COVID-19 vaccination. These models will follow the same structure as the primary outcome model, controlling for baseline values and including relevant covariates.

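### The only random effect specified is a two-level participation-mode intercept, which does not model the correlation between members of a randomised dyad

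*Combined protocol and SAP*

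**What the plan says.** - **Randomised unit** (Methods, Procedures, Randomization): "A randomization unit consisted of either an individual participating alone or with a partner to form a dyad". Mode was chosen before allocation. The same section also says "Randomization took place at the individual level".
- **Purpose of the random effect** (Statistics Analysis Plan, Primary Outcome Analysis, 2) Model Construction, a): the models "include a random effect to account for participant clustering".
- **Definition of the random effect** (same heading, b) Model Specification): "Random Effects: Participant cluster (random intercepts for participation mode: individual vs dyad". The fixed effects are treatment, the baseline outcome and covariates. Participation mode is not among them.
- **Secondary outcomes** (Secondary Outcome Analysis): "These models will follow the same structure as the primary outcome model, controlling for baseline values and including relevant covariates". One of these is binary at participant level: "COVID-19 testing receipt (proportion of participants received COVID-19 testing during the past 30 days".
- **Delivery** (Intervention Group Activities, Intervention Component #1): "Participants who chose to participate as a dyad attended the sessions together", and "Each LHW outreach session, lasting under 1 hour, involved 2 to 6 participants".

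The documents give no dyad or unit identifier, no `SUBJECT=` term, no robust variance and no within-dyad covariance structure.

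**The concern.** Partners allocated as one unit share an arm. If their outcomes are still correlated after adjustment for baseline and covariates, two partners carry less information about treatment than two unrelated people, and the model has to allow for that.

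A random intercept for participation mode does not. It gives one common shift to every dyad participant in the trial and another to every solo participant. Two partners are then modelled as no more alike than two strangers in different dyads. Their extra correlation stays in a residual that is treated as independent. A variance component based on two levels is also barely estimable, although that is secondary to the unmodelled pairing.

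Some positive correlation is plausible: partners are friends or relatives, and in the intervention arm they shared sessions. If the literal model was run, confidence intervals would be too narrow and p-values too small.

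**Working it through.** The documents state no SE, intraclass correlation, power or sample-size calculation, so there is no figure of the plan's own to reproduce. The check is structural, followed by a range for the size.

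**Inputs**
- From the documents: N = 247; the unit is a solo participant or a dyad; one outcome time point, week 16.
- Assumed, because not stated: share of participants in dyads, p; residual within-dyad correlation, rho (equal in both arms); 1:1 allocation; two-sided 5% test; model-based SEs.

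**Formula.** In an arm of n participants, a share p in dyads gives np/2 pairs, and each pair adds 2 × rho × sigma² to the variance of the arm total. The variance of the arm mean is (sigma²/n)(1 + p × rho). Hence:
- design effect DE = 1 + p × rho;
- true SE / reported SE = sqrt(DE);
- actual type I error = 2 × (1 − Phi(1.96 / sqrt(DE)));
- effective N = 247 / DE.

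For p = 0.5, rho = 0.3: DE = 1.15; sqrt(1.15) = 1.072; 1.96 / 1.072 = 1.83, so type I error is 6.8%; 247 / 1.15 = 215.

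| p | rho | SE excess | Type I error | Effective N |
|---|---|---|---|---|
| 0.10 | 0.1 | 0.5% | 5.1% | 245 |
| 0.25 | 0.1 | 1.2% | 5.3% | 241 |
| 0.25 | 0.3 | 3.7% | 5.9% | 230 |
| 0.5 | 0.1 | 2.5% | 5.6% | 235 |
| 0.5 | 0.3 | 7.2% | 6.8% | 215 |
| 0.5 | 0.5 | 11.8% | 8.0% | 198 |
| 0.7 | 0.5 | 16.2% | 9.2% | 183 |

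**Retention.** If 80% respond independently at week 16, some dyads become singletons and p is replaced by 0.8p. At (0.5, 0.3), DE = 1 + 0.4 × 0.3 = 1.12 and type I error is 6.4%. At (0.7, 0.5), DE = 1 + 0.56 × 0.5 = 1.28 and it is 8.3%.

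**Simulation, continuous outcome.** 10,000 null trials per setting, N = 247, allocation by unit, baseline-adjusted, REML; Monte Carlo error about ±0.4 points.

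| (p, rho) | Random intercept for mode (literal) | Random intercept per unit, mode fixed |
|---|---|---|
| (0.10, 0.1) | 5.0% | 4.8% |
| (0.25, 0.3) | 5.9% | 5.2% |
| (0.5, 0.1) | 5.6% | 4.9% |
| (0.5, 0.3) | 6.9% | 5.1% |
| (0.5, 0.5) | 7.7% | 4.9% |
| (0.7, 0.5) | 8.8% | 4.7% |

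With no true mode effect, the mode variance was estimated as zero in 63–68% of trials. Cluster-robust SEs by unit gave 4.9–5.3%.

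A second simulation without baseline adjustment (4,000 trials per setting; 1.96 × sqrt(0.05 × 0.95 / 4,000) is about ±0.7 points) gave, for mode against unit intercept, 6.7% and 5.1% at (0.4, 0.3), 8.2% and 5.9% at (0.4, 0.5), 7.8% and 4.6% at (0.8, 0.3), and 10.1% and 5.4% at (0.8, 0.5). With rho = 0 both were near nominal. At (0.8, 0.5) the mean model SE was 0.127 SD with the mode intercept and 0.149 SD with the unit intercept, against an empirical 0.151 SD.

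**Simulation, binary outcome** (30% prevalence assumed). At (0.25, 0.3), (0.5, 0.1), (0.5, 0.3), (0.5, 0.5) and (0.7, 0.5), a mode-only logistic model gave 5.4%, 5.6%, 6.7%, 8.2% and 9.2% (10,000 trials). Robust SEs by unit gave 4.6–5.2% (10,000 trials). A random-intercept logistic model by unit gave 2.4–4.3% (1,000 trials, about ±1.4 points), with its variance estimated near zero in up to 27% of trials.

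**The case against.** The strongest reply is that the specification is only badly worded. The term is labelled as a participant cluster, its stated purpose is clustering, and the bracket echoes the definition of the randomisation unit. It may therefore mean an intercept per unit of size one or two. On that reading the model is sound and one line needs correcting. This stands as a possibility: the documents do not show that a wrong SE was reported. It does not rescue the text, because the only definition given is a two-level term and nothing else identifies the unit.

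The size is also uncertain. Neither p nor rho is documented, and at the low end the effect is trivial. The covariates include cultural group, language, household type, county case rate and a place index. Partners may share several of these, so the residual correlation could be well below the raw one. Shared sessions occurred in one arm only, so a common rho may overstate the effect. With p = 0.5 and rho of 0.3 (intervention) and 0.1 (control), DE = 1 + 0.5 × (0.3 + 0.1) / 2 = 1.10, giving an SE excess of 4.9% and a type I error of about 6.2%, against 7.2% and 6.8%. All of this stands. It affects the size and leaves the direction unchanged.

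For the binary outcome, the upper end of the random-intercept logistic results (4.3%) is compatible with 5% given Monte Carlo error. The preference for a marginal model there is therefore a recommendation and not a necessity.

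Finally, the shared arm is inferred from the unit definition and is well supported by joint session attendance. The sentence on individual-level randomisation conflicts with it and needs reconciling.

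**Conclusion.** The concern holds. Followed literally, the plan fits a model that leaves within-dyad correlation unmodelled, so the treatment SE is too small whenever that residual correlation is positive. Over the assumed range, p = 0.10 to 0.7 and rho = 0.1 to 0.5, the SE excess runs from 0.5% to 16.2% and the true type I error from 5.1% to 9.2%. If dyads are few or rho is small, the effect is negligible.

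These figures assume that the literal model was run, that partners share an arm and both contribute week-16 data, and that SEs are model-based. The continuous simulations also treat the score as Gaussian, since the plan gives no distribution or link. This should be fixed. Confidence is medium, because only the sponsor can say which model was fitted.

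**What to change.** - Define the cluster as the randomised unit: a dyad identifier, with each solo participant as a unit of one. For outcomes modelled as continuous, use `RANDOM INTERCEPT / SUBJECT=unit_id`.
- For binary testing receipt, prefer a marginal model or cluster-robust SEs by unit. The random-intercept logistic model tended to be conservative with clusters of one or two.
- If participation mode is kept, enter it as a fixed effect.
- State which model was run. If mode was the grouping factor, re-estimate the primary and secondary results. If the unit was, correct the wording.
- Reconcile the statement of individual-level randomisation with the definition of the unit.
- Report the numbers of dyads and solo units randomised and analysed at week 16.

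The cost is a changed `RANDOM` statement, a robust-SE option for the binary outcome and a short text correction. An identifier linking partners is needed. The documents do not mention one, but a link must have existed to allocate a dyad as one unit. Intervals will widen slightly if rho is positive. Session grouping in the intervention arm is a separate source of clustering that this change does not address.

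### Does the plan need to say which survey and which month define the county case-rate covariate?

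*Combined protocol and SAP*

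**What the plan says.** Under Primary Outcome Analysis, item 3c (Community-Level Covariates), the SAP lists "COVID cases per 100,000 populations (matched participants' county and month of survey date", next to a county-level place index. The survey is in the singular and is not identified.

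The Study Design section gives five candidate dates: "assessments at baseline, weeks 4, 8, 12 and 16". Two of them feed each analysis record. Item 2a describes a "multilevel mixed effects model to analyze the primary outcome at week 16 by treatment group", and adds: "These models were adjusted for the baseline value of the outcome variable".

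Secondary Outcome Analysis includes "COVID-19 testing receipt (proportion of participants received COVID-19 testing during the past 30 days", also at week 16. It says of the secondary models: "These models will follow the same structure as the primary outcome model, controlling for baseline values and including relevant covariates". The case rate is therefore carried into the testing-receipt model by implication; it is not listed there again. Neither the SURE scores nor testing intention has a stated recall window.

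**The concern.** A reader cannot rebuild the covariate from the text with certainty. The survey could be baseline or week 16. The month could be the calendar month containing the survey date or the 30 days leading up to it.

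For testing receipt the choice has a visible consequence. The outcome counts tests in the 30 days before the week-16 survey, and cases that occur after the survey cannot have prompted those tests. A calendar month that runs on past the survey, or one that closed months earlier, measures epidemic intensity at partly or wholly the wrong time. A covariate that tracks the outcome less closely explains less of it, so the testing-receipt model could lose some precision. Reproducibility and that possible loss are all that is at stake.

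**Working it through.** The documents give no figure on this point to reproduce, so the check is a count of days.

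**Inputs.** The look-back is 30 days (Secondary Outcome Analysis). The outcome survey is at week 16 (item 2a), taken as 16 × 7 = 112 days after the baseline survey. Three things are assumed: 30-day months, the survey day counted as part of the look-back, and survey days spread evenly over the month. The last affects only the averages.

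**Calendar month of the week-16 survey.** For a survey on day d:
- Share of the look-back inside the month = d/30. Day 1 gives 1/30 = 3%, day 15 gives 50% and day 30 gives 100%. The mean is (1 + 2 + … + 30)/(30 × 30) = 465/900 = 52%.
- Share of the month falling after the survey = (30 − d)/30, from 0% to 97%, with mean 435/900 = 48%.
- Less than half the look-back is covered when d is 1 to 14, which is 14 of 30 days.

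**Thirty days ending on the week-16 survey.** Overlap is 100% by construction.

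**Calendar month of the baseline survey.** The month ends at most 29 days after baseline. The look-back opens on day 112 − 29 = 83. Overlap is 0%, with 83 − 29 − 1 = 53 to 83 − 0 − 1 = 82 days in between.

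**Check with real calendars.** Placing baseline on each of 1,095 consecutive dates (2021–2023, assumed because the documents give no calendar dates) gave the same results: 3–100% with mean 52%, 100%, and 0%. If the survey day is not counted, the week-16 calendar-month figures become 0–100% with mean 49%. The baseline figure stays at 0% even if the week-16 survey is 28 days early or late.

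**What the overlap does to the treatment comparison.** This cannot be computed, because no case rates or results are given. The usual linear residual-variance formula does not settle it. Testing receipt is a yes/no outcome, and the model is fitted in GLIMMIX with no stated link. An illustration under a logit link used a simulation scaled to n = 247, with a covariate explaining about 10% of outcome variance (assumed). The table shows the treatment log-odds by the correlation r between the covariate used and the aligned one.

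| r | SE | z |
|---|---|---|
| 1 (aligned) | 0.271 | 1.81 |
| 0.65 | 0.262 | 1.76 |
| 0 | 0.256 | 1.79 |

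Poorer alignment gives a smaller standard error. The estimate also moves towards zero, from 0.49 to 0.46, and z moves by no more than 1.81 − 1.76 = 0.05. So a better-aligned covariate does not necessarily shrink the standard error, and nothing here points to a material loss.

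**The case for a change.** The best case for acting is that the omission can be verified and would cost one sentence to repair. The SAP says its covariate and model details are supplied, and this one is not. Baseline cannot be ruled out, since most of the covariates listed alongside, such as education and household type, read as baseline characteristics. Nor does choosing week 16 settle the alignment question: on the calendar-month reading the overlap still depends only on the day of the month.

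The omission and the day counts stand, but the ambiguity is narrower than five surveys and two windows suggest. Weeks 4, 8 and 12 play no part in the model as written. Of the two dates that do, week 16 is the likelier because the outcome is measured then. The ordinary sense of the month of a date is the calendar month containing it, and the trailing 30 days is a looser reading. Complete alignment and no alignment are therefore the ends of a range whose natural value lies between them.

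An extra run of the testing-receipt model on a trailing 30-day rate has been suggested. It would be post hoc, would need sub-monthly county counts or a weighted average of adjacent months, and would leave the planned result unchanged. No benefit from it has been shown.

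**Conclusion.** No change to the plan is called for. This is a missing descriptive detail about one adjustment covariate. The natural reading, the calendar month of the week-16 survey, is workable, and the analysts already know what they used.

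On that reading the covariate month covers 3–100% of the testing look-back, with mean 52% if survey days are evenly spread. The 0% figure applies only if the baseline month was used. These overlaps affect one secondary model. Allocation is randomised, so an imperfectly timed county rate does not confound the comparison. Under a logit link the adjusted odds ratio does shift a little with the quality of the covariate, but that reflects what the estimate conditions on; it is not an imbalance between the groups. The SURE and intention outcomes have no stated recall window against which to claim a mismatch.

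The conclusion rests on week 16 falling about 112 days after baseline and on the case rate being carried into the testing-receipt model through the shared model structure. Naming the survey and the month when results are reported would help a reader reproduce the model, but it would not alter the analysis.

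### Does a 30-day look-back at week 16 make the testing-receipt outcome miss the effect of lay health worker outreach?

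*Combined protocol and SAP*

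**What the plan says.** The Secondary Outcome Analysis section lists three secondary outcomes at week 16. Testing receipt, the "proportion of participants received COVID-19 testing during the past 30 days", is the only behaviour among them. The other two are an intention and a SURE score, and the primary outcome is also a SURE score. The secondary models follow the primary model, with adjustment for the baseline value and the listed covariates.

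Participants Recruitment and Payment Incentives sets the week-16 survey apart from the others. The incentive there is "for the final survey at week 16 (15-20 minutes) for outcome evaluation", whereas the earlier contacts are a "brief survey at weeks 4, 8, and 12 (5-10 minutes" each. The items in those brief surveys are not listed, and the SAP describes no analysis of them.

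The text messages are identical in both arms (Control Group Activities), so LHW outreach is the whole difference between them. Under Intervention Component #1, "Sessions were spaced approximately 1 month apart, with follow-up calls conducted within 2 weeks after each session", and "the 4 LHW outreach contacts (group sessions and follow-up calls) were completed within 6 to 8 weeks". The sessions aimed at, among other things, "informing them about free testing availability, and motivating them to get tested". Each session closed with an action item that might lead participants to "if appropriate, take steps toward getting tested (such as identifying test sites". The lag from baseline or randomization to the first session is not given.

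**The concern.** Outreach that succeeds in prompting testing might be expected to do so during the sessions or soon after them. If outreach began shortly after baseline, the week-16 question looks back over a period that opens weeks after the last LHW contact. A participant who was tested after the first session and not again in the final 30 days counts as not tested.

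On that reading, the planned comparison cannot tell two situations apart: outreach that never changed testing, and outreach that raised testing for a while before the rise faded. The SAP does not say which of these a null result would support. The surveys at weeks 4, 8 and 12 seem to offer data that could help, and they go unused. At stake is the interpretation of the trial's one behavioural outcome.

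**Working it through.** **Inputs.** The 30-day look-back and the week-16 analysis come from Secondary Outcome Analysis. The course length of 6 to 8 weeks and the session spacing come from Intervention Component #1. The 247 participants and the survey weeks come from Study Design. Day 0 is baseline, and the week-16 survey is assumed to fall on day 112.

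**1. The plan's own duration.** Sessions one month apart (28 to 31 days) plus a last call up to 14 days later give 28 + 14 = 42 to 31 + 14 = 45 days, or 6.0 to 6.4 weeks. This lies inside the stated 6 to 8 weeks (42 to 56 days).

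**2. The window.** 16 × 7 = 112 and 112 − 30 = 82, so the window is days 82 to 112. It covers 30/112 = 27% of follow-up.

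**3. Outreach against the window.** Outreach starting on day s with length L ends on day s + L. Days inside the window = max(0, s + L − 82), for courses that end by day 112. This is zero when s ≤ 82 − 56 = 26 (8-week course) or s ≤ 82 − 42 = 40 (6-week course).

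| First session | 6-week course: end day, days in window | 8-week course: end day, days in window |
|---|---|---|
| Day 0 | 42, none | 56, none |
| Day 14 | 56, none | 70, none |
| Day 28 | 70, none | 84, 2 |
| Day 42 | 84, 2 | 98, 16 |
| Day 56 | 98, 16 | 112, 30 |

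A survey completed 7 days early or late moves the 8-week threshold to day 19 or day 33. If outreach had to end by day 112, it began by day 56 (8-week) or day 70 (6-week). At least 82 − 56 = 26 or 82 − 70 = 12 days of it then precede the window. No section states that end date, although it is plausible.

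**4. What the overlap measures.** It counts days of delivery inside the window, not the share of the effect that is captured. An outcome assessed after an intervention has ended has zero overlap by design. With a day-0 start, the window opens 82 − 56 = 26 to 82 − 42 = 40 days after outreach ended, and it measures whether testing was sustained. The documents give no testing rates, effect size or evidence of fading, so the overlap cannot be turned into a loss of effect.

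**5. What an added model could show.** Suppose the brief surveys asked the same item, which is not stated. Assume a 1:1 split (247/2 = 123.5 per arm), control rates p of 10%, 20% and 30%, full response and no dyad clustering.

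- Half-width of the arm difference at one survey = 1.96 × √(2p(1 − p)/123.5) = 7.5, 10.0 and 11.4 points.
- Separating no effect from a faded effect needs the early-minus-week-16 contrast. With within-person correlation r, its half-width is the single-survey value × √(2(1 − r)). The factor is 0.894 at r = 0.6 and 1.265 at r = 0.2. The range is 7.5 × 0.894 = 6.7 to 11.4 × 1.265 = 14.4, or about 7 to 14 points.
- Power for a true 10-point rise at one survey = Φ(0.10/SE − 1.96), with SE = √([p(1 − p) + (p + 0.1)(0.9 − p)]/123.5) = 4.5, 5.5 and 6.0 points. This gives about 60%, 45% and 38%.

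Non-response and dyad clustering would generally make these figures worse. The added model would usually leave the ambiguity where it was.

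**The case for a change.** The strongest case for acting is that the calendar facts are sound and the cost is small. Whenever outreach ended by week 16, its first session came before the window, and with a prompt start all of it did. The sessions were meant to motivate testing, so a test taken soon after a session is a natural target, and the planned outcome does not count it. If the brief surveys carried the item, four 30-day look-backs would cover all 112 days instead of 27%, using data already collected and without touching the planned inference.

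The calendar facts stand. So does the point that a null at week 16 would not rule out an earlier, unsustained rise. The step from there to a change in the plan does not. The extra model depends on survey content that the documents do not describe. It would be post hoc, since the section reports the primary analysis as already conducted, and step 5 of the working shows it would seldom settle the question. Relabelling the outcome as testing in the 30 days before week 16 adds almost nothing, because its definition already gives both the time point and the look-back.

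The late window also has reasons in its favour. The curriculum taught repeated testing, and a companion outcome is the intention to test as often as needed, so recent testing at the end of follow-up is a coherent target. A 30-day item fits the county case rate, which is matched to the month of the survey, and it allows adjustment for the same item at baseline. The plan gives no rationale of its own for 30 days.

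**Conclusion.** No change is needed. The choice of window is a fair trade-off: the plan measures recent testing at the designated outcome survey and gives up information on short-lived testing earlier in follow-up. The comparison is valid between randomized arms for the quantity it defines.

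The limit on interpretation is real but small. It concerns one secondary outcome, leaves the primary SURE analysis untouched, and comes to this: a null result describes testing in the last 30 days of follow-up and does not show that outreach never prompted testing. The outcome definition already lets a reader see that.

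The timing thresholds (day 26 and day 40) assume that week 16 is counted from baseline and that the survey was answered on day 112. That some outreach always precedes the window assumes further that outreach ended by week 16. The precision figures rest on assumed control rates of 10% to 30%, within-person correlations of 0.2 to 0.6 and equal allocation. Any effect of the window on the trial's result cannot be quantified from the documents.
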